APPENDIX A –PUP™ SOCK LABEL

APPENDIX B - SCHEDULE OF STUDY VISITS

	DAY 1 ADMISSION (Day/Week/Month #) ^a	VISITS ON DAY 1 & EVERY DAY THROUGH LENGTH OF STAY	VISIT ON PATIENT EARLY WITHDRAWAL	VISIT ON PATIENT DISCHARGE
Informed Consent	X			
Medical History	X			
Complete Physical Exam	X			
Abbreviated Physical Exam		X	X	X
Weight	X	X	X	X
Administration of PUP™ Fall Prevention System	X			
Counting of Returned PUP™ socks		X	X	X
Initiate Subject Diary	X			
Subject Diary Review		X		X
Adverse Experiences		X	X	

^a ±2 days

**APPENDIX C - PUP (PATIENT IS UP) SYSTEM
CASE REPORT FORM – OHIO STATE UNIVERSITY**

PARTICIPANT INFORMATION		
Participant ID		
Inclusion/exclusion criteria *Patient must meet all fall risk criteria to be eligible for the study	Met all 	Not met* 
Date of Informed IRB Consent		
Gender	 Male	 Female
Date of Enrollment into Fall Prevention System		

EARLY DISCONTINUATION OF STUDY	
Date of discontinuation from study	
Reason for discontinuation	
  Subject withdrawal  Subject not compliant 
  Intermittent wearing of the sock  Refusal after enrollment to wear the sock  Repeatedly engaging in activity which defeats the integrity of the electronic circuitry of the sock  Sponsor request for early termination of study  Protocol Violation: _____

FINAL STUDY OUTCOME

Investigator's Statement: I have reviewed the data recorded in this CRF and confirm that the data are complete and accurate

Investigator (Full name): _____

Investigator Signed? **Signature Date:** _____

## Palarum Data

### Primary dataset

- 732 entries with multiple enrollment and unenrollment dates (technical error)
- 569 patients after data cleaning multiple entries by limiting data to first enrollment and last unenrollment
- Variables included – floor, unit, enrollment date, unenrollment date. From these we calculated length of stay.

Variable	Level	Total (n=569)
OSU unit	Missing	3 (1%)
	10 East	127 (22%)
	10 South	108 (19%)
	8 East	64 (11%)
	8 South	102 (18%)
	9 East	81 (14%)
	9 South	84 (15%)
Length of Stay (Days)	Median [IQR] (min, max)	2 [1, 3.9] (0, 127.2)

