HIPAA	Health Insurance Portability and Accountability Act of 1996
HUC	Health Pod Coordinator/UCA Monitor
ICF	Informed Consent Form
IEC	Independent Ethics Committee
IRB	Institutional Review Board
IRL	In Room Locator
IRT	In Room Tablet
PI	Principal Investigator
PLS	Palarum Local Server
PUP™	Patient is Up Fall Prevention System
RSSI	Receive Signal Strength Indicator
RTLS	Real Time Location System
PCS	Palarum Cloud Service
SAE	Serious Adverse Experience
WIRB	Western Institutional Review Board

PROTOCOL SYNOPSIS

TITLE	Testing the Effectiveness of a Fall Prevention System
SPONSOR	[name] PhD
FUNDING ORGANIZATION	Palarum, LLC
NUMBER OF SITES	1 Site on 3 floors of the Ohio State University Wexner Center Brain and Spine Hospital; (8 South, 9 South, 10 South, 8 East, 9 East & 10 East)
RATIONALE	
Each year, between 700,000 and 1,000,000 people in the United States fall in a healthcare environment (Agency for Healthcare Research and Quality, 2015). Falls can have a widespread and significant impact on health, can be deadly, and often result in high costs. Falls with serious injury are consistently among the Top 10 sentinel events reported to The Joint Commission's Sentinel Event database (The Joint Commission, 2015). The average 200-bed hospital might log 300 patient falls a year (based on 5 patient falls per 1000 patient days), which results in \$10,200 per fall in medical costs annually – or more than \$3 million. (Agency for Healthcare Research and Quality)
 
The best way to reduce the number of falls is to prevent them. A whole marketplace of bed and chair alerts and other devices has been developed to address the need, yet the numbers increase. On a busy patient floor, nurses lose valuable seconds just figuring out which patient's bed alert is sounding. We expect research to show that the Palarum PUP™ System reduces the incidence of falls.

STUDY DESIGN	Single arm trial
PRIMARY OBJECTIVE	To determine if the fall rate (as measured by falls per 1000 patient days) for patients designated “fall risk” decreases with the use of the intervention (Patient is UP fall prevention technology [PUP™]) when compared to historical NDNQI data for the prior 12 months (“Benchmark Data”) from nursing units where the intervention is being undertaken.

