	
Android tablet (IRT), a nurse station Android monitor (HUC), a local server (PLS), a cloud server (PCS), a Bluetooth Low Energy beacon(s), an Android smart notification device, and an e-textile sock connected sensor transmitter (PUP™ sock).
 
The PUP™ sock monitors and transmits pressure, force, acceleration and motion data to IRT and PLS, and HUC and PCS. This data is evaluated and validated by an Android application on the IRT to determine whether or not a fall risk patient is standing unaccompanied by a caregiver. If a monitored patient is standing unattended, the PLS locates and alerts the Smart Notification Devices of the five (5) closest healthcare providers and the HUC using the beacon technology.
 
Alerts are terminated by the Smart Notification Device and PLS based on caregiver proximity to the patient. All data, alerts, suspensions, terminations and notifications are recorded by the PCS. On a daily basis, PCS reports are produced which contain data for each patient enrolled, number of alerts, excessive alerts, and caregiver response time, as well as summaries by Pod and entire facility.
 
All Brain and Spine Hospital patients will be evaluated as to fall risk using the current fall risk assessment procedures employed by OSU Medical Center and administered in the usual and customary fashion upon evaluation on the floor and Pod.
 
Any patient fall is to be reported and evaluated following current processes and procedures developed by the OSU Brain and Spine Institute as maintained with IHIS.
 
If a fall risk patient is admitted to the unit and is not otherwise disqualified by the Study Exclusion Criteria, the patient and/or LAR in form of a Patient Consent document, will be given information about and the opportunity for the patient to participate in the Study. If the patient or legal surrogate declines participation, the patient will receive standard of care provided prior to the Study.
 
Upon receiving a consent to participate, the patient will be fitted with a monitored PUP™ sock sized to the patient's foot from the Study inventory, and thereafter enrolled by a caregiver in the Palarum Fall Prevention System using an Android application on the IRT. The Palarum Fall Prevention System and PUP™ sock thereafter monitor the patient's activity 24x7 throughout the patient's entire length of stay. During the patient's stay, the PUP™ sock will be evaluated daily for proper fit, patient comfort, and patient safety. Upon discharge or transfer, the patient is un-enrolled from the system again

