--	---

	
utilizing the IRT. All patient relevant fall data, including system performance, is collected and stored in the PCS for future study and evaluation. Any patient fall is to be reported and evaluated following current OSU Medical Center processes and procedures independent of the Palarum Fall Prevention System.
 
Technical support for the Palarum Fall Prevention system is available by phone at [name] [contact] and email, [contact], 24x7. If there is a Palarum Fall Prevention System outage each Intervention Group Pod should follow policies related to downtime procedures for fall risk patients.

CONTROL PRODUCT, DOSE AND ROUTE OF ADMINISTRATION	N/A
DURATION OF SUBJECT PARTICIPATION AND DURATION OF STUDY	Duration: Once a patient has been placed in the fall risk protocol, the patient will remain in the study until a nurse removes the patient from risk fall status or the participant has been discharged from the hospital.
CONCOMITANT MEDICATIONS	
Allowed: YES
 
Prohibited: NONE

EFFECTIVENESS EVALUATIONS	
Effectiveness evaluation data will be collected by the Palarum Fall Risk System, and incorporated and integrated with patient diagnosis, co-morbidities, and other medical data within REDCap including:
 
 1. Enrollment Data 
 a. Patient Identifier/MRN b. Patient Weight c. Patient Sock Size (S-M-L-XL) d. Sex e. Pod and Room/Bed f. Date g. Time h. Sock Number i. Sensor Number 2. Event Logs 3. Time of stand alert 4. Time to clear 5. Who cleared stand 6. Manual or Automatic termination 7. Accelerator and Gyroscopic Data surrounding each stand event

	8. Pressure on foot 9. Motion of patient
PRIMARY ENDPOINT	Fall rate per patient days within the study sample population
SECONDARY ENDPOINTS	
As collected by the Palarum Fall Prevention System, validated by manual audits of thereof, and integrated with REDCap,
 
 • Rate of false alerts • Rate of fall related patient safety events • Time to respond to alert • Pressure on foot • Motion of patient • Alert fatigue analyzed and measured by alert responded/alerts generated over time. • Notification system alerts only the closest five caregivers when a fall risk patient is up • Time to staff notification (latency) when a fall risk patient is up and unattended • Time to clear data • Identification of caregiver clearing alert • Determination of manual or automatic termination

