OTHER EVALUATIONS	N/A
SAFETY EVALUATIONS	Incidence of adverse events arising use of device
PLANNED INTERIM ANALYSES	N/A
STATISTICS Primary Analysis Plan	
The primary endpoint for this study is the number of patient falls. This will be expressed as a falls incidence rate, i.e., number of falls per patient days where patient days are counted from the initiation of the PUPTM System until discharge or removal from the fall risk protocol. Using a one-sided one-sample test for Poisson means, we will test whether the observed fall rate is less than the historical rate of 0.004. This test will be conducted at the alpha=0.1 level. Results will be presented as the fall rate and the corresponding one-sided 90% confidence interval which will provide an upper bound for the fall rate.

Rationale for Number of Subjects	The primary endpoint of the trial is the patient fall rate per patient days. Comparing to a historical rate of 0.004 using a one-sided test of Poisson means, we have at least 70% power to detect a 25% reduction in the fall rate at alpha level 0.1 with 2360. Assuming a dropout rate of 5%, we will enroll 2500 patients into the study.
---	---

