13.2 Analysis of Primary Endpoint

The primary endpoint for this study is the number of patient falls. This will be expressed as a rate per patient days where patient days are counted from the initiations of the PUP™ System until discharge or removal from the fall risk protocol. Using a one-sided one-sample test for Poisson means, we will test whether the observed fall rate is less than the historical rate of 0.004. This test will be conducted at the alpha=0.1 level. Results will be presented as the fall rate and the corresponding one-sided 90% confidence interval which will provide an upper bound for the fall rate.

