#### Study Objectives

- To determine if the fall rate (as measured by falls per 1000 patient days) for patients designated “high fall risk” decreases with the use of the intervention (Patient is Up fall prevention technology [PUP]) when compared to historical NDNQI data for the prior 12 months (“Benchmark Data”) from nursing units where the intervention is being undertaken.
  - We ran a one-sided one-sample test for Poisson means using fall events (0 falls) and length of stay (2211.6 days) to estimate the fall rate
  - Results are presented as the fall rate and the corresponding one-sided 90% confidence interval which provides an upper bound for the fall rate.
    - 0 falls (Upper bound 1.04) per 1000 days
  - This fall rate was lower than the historical rate of 4 falls per 1000 days
- To reduce the incidence of false alerts, <5%. Our goal is a high reliability notification system.
  - No data collected for this
- To provide positive alert reliability of 95%. Our goal is to reduce alert fatigue with nurses. To determine number of alerts sent out; what is the frequency of these patient safety events (i.e.), fall risk patient up, out of bed, unassisted
  - No data collected for this
- To gather compliance data and response times from alert to caregiver response.

- Stand Time captured in seconds

Variable	Level	Total (n=4999)
Stand (seconds)	Median (IQR) (min, max)	24.0 (5.0, 64.0) (1.0, 593.0)

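### Given 0 falls, the reported upper bound rests on device-log patient-days that the SAP does not check against discharge or fall-risk removal

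*SAP*

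**What the plan says.** **Protocol.** The Synopsis (Statistics, Primary Analysis Plan) states that "patient days are counted from the initiation of the PUPTM System until discharge or removal from the fall risk protocol". Section 13.2 gives the same end point: "until discharge or removal from the fall risk protocol". The Synopsis entry on duration of participation agrees: "the patient will remain in the study until a nurse removes the patient from risk fall status", or until discharge. Sections 7.10 and 9.4 make un-enrolment a step at discharge. The Synopsis (Method of Use) adds transfer: "Upon discharge or transfer, the patient is un-enrolled from the system". No section ties un-enrolment to the removal of fall-risk status. Method of Use also has falls reported through hospital processes that are independent of the device. Section 13 says the SAP will record any change to the planned analysis.

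**SAP.** The Primary dataset section starts from "732 entries with multiple enrollment and unenrollment dates (technical error" and reduces these to "569 patients after data cleaning multiple entries by limiting data to first enrollment and last unenrollment". Length of stay is calculated from those device dates: median 2 days, quartiles 1 and 3.9, range 0 to 127.2. Under Study Objectives the primary test uses "fall events (0 falls) and length of stay (2211.6 days) to estimate the fall rate", and the reported upper bound is 1.04 per 1000 days. The 0 falls come from the Palarum Secondary dataset. The hospital variables listed under Admission Data include no discharge or fall-risk-removal date. The hospital Falls Data section holds a history-of-falling field, not in-study fall reports. Under Data discrepancies, 48 device patients are absent from the hospital data.

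**The concern.** The end of patient-days has moved from a hospital event to a device log-out. The SAP neither declares this as a change nor reports a check of it. The log-outs come from records in which the SAP itself found multiple dates that it puts down to a technical fault.

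What is at stake is the upper bound, which section 13.2 commits to reporting. With no falls, the bound depends only on alpha and the number of days, so an error in the days passes straight into it. Days counted beyond the protocol's end point make the bound too low, and days cut short make it too high. The zero count matters as much: it has the same device source, and the SAP describes no reconciliation with hospital fall reports.

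**Working it through.** **Inputs.** Falls x = 0 and T = 2211.6 days (SAP, Study Objectives); alpha = 0.1, one-sided, and historical rate 0.004 per day (Protocol 13.2); longest span 127.2 days and n = 569 (SAP, Primary dataset); 48 device patients not in the hospital data (SAP, Data discrepancies).

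**1. Reproduce the reported bound.** The exact one-sided Poisson upper bound is chi-square(0.9; 2(x+1)) / (2T). With x = 0 it reduces to −ln(0.1)/T = 2.3026/2211.6 = 1.041 per 1000. This matches the SAP's 1.04.

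**2. Compare the two rules.**

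| Situation | Device count against protocol count |
|---|---|
| One stay, un-enrolled at discharge | Same |
| Repeated enrolments within one stay | Same; the protocol also counts the gap |
| Span bridges separate admissions | Device count longer |
| Fall-risk status removed before log-out | Device count longer |
| Log-out late or missed | Device count longer |
| Un-enrolled at transfer, still in hospital and at fall risk | Device count shorter; bound conservative |

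The start agrees under both rules. The net direction of any difference cannot be read from the documents.

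**3. The longest span.** 127.2/2211.6 = 5.8% of all days. Without it, T = 2211.6 − 127.2 = 2084.4 and the bound is 2.3026/2084.4 = 1.10 per 1000.

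**4. Other values of T, still with 0 falls.** The changes in T are assumptions, because the documents give no hospital end dates.

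| Assumed change in T | Days | Bound per 1000 |
|---|---|---|
| +10% | 2432.8 | 0.95 |
| none | 2211.6 | 1.04 |
| −10% | 1990.4 | 1.16 |
| −25% | 1658.7 | 1.39 |
| −50% | 1105.8 | 2.08 |

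**5. When the comparison with 4 per 1000 would fail, with 0 falls.** The bound reaches 4 at T = 2.3026/0.004 = 575.6 days, which is 26% of 2211.6. About 74% of the days would have to be invalid. At T = 2211.6 the exact p-value is exp(−0.004 × 2211.6) = exp(−8.846) = 0.00014.

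**6. Dependence on the count, at T = 2211.6.**

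| Falls | Bound per 1000 | One-sided p against 4 per 1000 |
|---|---|---|
| 0 | 1.04 | 0.00014 |
| 1 | 1.76 | 0.0014 |
| 4 | 3.61 | 0.060 |
| 5 | 4.19 | 0.125 |

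A single fall moves the bound more than dropping the longest span does. Five falls would take it above 4.

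**The case against.** The strongest reply is that un-enrolment is the protocol's own discharge step (7.10, 9.4), so the proxy is sound by design. Within a single stay, first enrolment to last un-enrolment is the cleaning rule closest to section 13.2, because that section also counts gaps between enrolments. Un-enrolment at transfer shortens the count and so errs on the safe side. It also suits a benchmark taken "from nursing units where the intervention is being undertaken". All of this stands. What remains is the absence of any check, and the cases in the table where the device count would run long.

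A reader might infer more than the documents support:

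- That 2211.6 days is inflated. No bridged admission, late log-out or early loss of fall-risk status is shown.
- That the 127.2-day span is an error. It is far above the upper quartile of 3.9, but a long stay is possible.
- That the technical fault invalidates the spans. The SAP's phrase most naturally describes the multiple dates, which the first-to-last rule was meant to resolve.
- That the denominator alone fixes the bound. This holds only given 0 falls.
- That falls were missed. The documents show that the source was the device file, not that it was incomplete.

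**Conclusion.** The point holds as an undeclared and unverified substitution in the primary denominator, not as a demonstrated error. Given 0 falls, it bears on the reported bound: 1.04 as published and 1.10 if the one identified outlying span were dropped. The correct figure cannot be computed from the documents. The denominator issue does not threaten the comparison with 4 per 1000, which survives with 0 falls as long as at least 576 days are valid.

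That assurance is conditional on the zero count. If hospital reports over the same window contained falls, the bound would rise, and at 2211.6 days five of them would reverse the comparison. The figures assume the exact Poisson model that the plan specifies and take the SAP's totals as given. The change should be made: it is specific and inexpensive, and it can move the figure the protocol promises to report.

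**What to change.** 1. Recompute patient-days from PUP initiation to the earlier of hospital discharge and removal of fall-risk status, using hospital dates. Count separate admissions separately. Make this the primary denominator.
2. Count falls over the same window from the hospital's fall reports.
3. Check the 127.2-day span first, then the other long spans.
4. For the 48 device patients with no hospital record (48/569 = 8.4%), attempt record matching. Where it fails, keep the device span and report the bound with and without these patients.
5. Report the present first-to-last device count (bound 1.04) as a sensitivity analysis, and state in the SAP that it departs from section 13.2.
6. Add a bound with days ended at transfer off the six pods only if usable unit-level times can be obtained. The SAP's Admission Data section says the unit, department and room fields supplied were not useful.

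**Cost.** One hospital extract of discharge times, fall-risk-status times and fall reports; record matching for 48 patients; and a rerun of a simple test. The recomputed days may move the bound either way, and any hospital-reported fall would raise it.

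### The SAP's 2211.6 patient-days run from first enrolment to last un-enrolment and do not apply the stop rule in protocol 13.2, so the upper bound of 1.04 falls per 1000 days may be misstated

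*SAP*

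**What the plan says.** Three places in the protocol set the same stop rule.

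- Section 13.2 counts days from the start of PUP "until discharge or removal from the fall risk protocol".
- The synopsis statistics row repeats this: "patient days are counted from the initiation of the PUPTM System until discharge or removal from the fall risk protocol".
- The synopsis row on duration of participation agrees: "the patient will remain in the study until a nurse removes the patient from risk fall status", or until discharge.

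The operating text does not carry that rule. The synopsis method of use has monitoring "24x7 throughout the patient's entire length of stay", and then "Upon discharge or transfer, the patient is un-enrolled from the system again". Section 7.5 has the socks worn for the whole stay. Sections 7.10 and 9.4 describe un-enrolment or log-out at discharge. None of these places names removal from fall-risk status as a reason to un-enrol.

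The SAP (Palarum Data, Primary dataset) starts from "732 entries with multiple enrollment and unenrollment dates (technical error") and reduces them to "569 patients after data cleaning multiple entries by limiting data to first enrollment and last unenrollment". Length of stay is calculated from those dates. The variables listed are floor, unit, enrolment date and un-enrolment date, with no date of removal from fall-risk status. Under Study Objectives the primary analysis is run "using fall events (0 falls) and length of stay (2211.6 days) to estimate the fall rate", giving an upper bound of 1.04 per 1000 days.

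**The concern.** The denominator in the SAP is defined by when the system was switched on and off for a patient. The denominator in 13.2 is defined by fall-risk status and discharge. The two agree only if staff un-enrolled patients when fall-risk status was lifted, and the operating text does not tell them to.

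With no falls observed, the point estimate is 0 whatever the denominator. The upper bound is then the only informative part of the primary estimate, and it depends on nothing but the number of days. A reader cannot tell whether 2211.6 days is the exposure that 13.2 defines. Section 13 says that the SAP will contain any modifications to the planned analysis. The SAP states its window openly but does not label it as a modification.

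**Working it through.** **Inputs.** 0 falls, 2211.6 days and a stated bound of 1.04 per 1000 (SAP, Study Objectives). One-sided alpha 0.1 and historical rate 0.004 per day (protocol 13.2). 732 entries for 569 patients, longest span 127.2 days (SAP, Primary dataset).

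**Step 1: reproduce the stated bound.** With 0 events the exact one-sided 90% Poisson upper bound is −ln(0.1)/T = 2.3026/T. At T = 2211.6 this is 0.001041 per day, or 1.04 per 1000, which matches the SAP. The exact p-value against 0.004 is exp(−0.004 × 2211.6) = exp(−8.846) = 0.00014.

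**Step 2: excess days.** Let f be the share of the 2211.6 days that 13.2 would not count. Cutting days cannot remove a fall, because there are none, so the bound becomes 2.3026/[2211.6 × (1 − f)]. The documents do not give f; the values below are assumptions.

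| Assumed f | Days left | Upper bound per 1000 | p against 0.004 |
|---|---|---|---|
| 0 | 2211.6 | 1.04 | 0.00014 |
| 10% | 1990.4 | 1.16 | 0.00035 |
| 20% | 1769.3 | 1.30 | 0.00084 |
| 30% | 1548.1 | 1.49 | 0.0020 |

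The printed figure is sensitive to small changes. It rounds to 1.05 once T falls to 2.3026/0.001045 = 2203.4 days, a loss of 8.2 days. One long span also matters: without the 127.2-day patient, the bound is 2.3026/2084.4 = 1.10 per 1000. That span may be a genuine stay, so this shows leverage and not an error.

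**Step 3: break-even.** The bound reaches 4 per 1000 at 2.3026/0.004 = 575.6 days. That requires f = 1 − 575.6/2211.6 = 0.74.

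**Step 4: the opposite direction.** Section 13.2 does not name transfer or early discontinuation as a stop. The method of use un-enrols at transfer, and section 11.1 allows discontinuation for non-compliance or withdrawal. Such patients may leave the SAP's count before the 13.2 endpoint. If 10% more days should have been counted (an assumption) and no falls occurred in them, T = 2432.8 and the bound is 2.3026/2432.8 = 0.95 per 1000. Any falls in that time would have to be counted as well.

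**Step 5: patients with several entries.** There are 732 − 569 = 163 surplus entries. The SAP attributes the multiple entries to a technical error. For a patient who stayed at fall risk through one admission, a single span across such a gap is what 13.2 prescribes. It is wrong only if the gap includes time off fall-risk status or between separate admissions. The SAP's hospital admission data also mention multiple admission times, so the second case is possible but not shown.

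**The case against.** The strongest defence is that no departure from 13.2 has been demonstrated. The duration row ends participation at removal or discharge, and un-enrolment is the natural system record of that end. Sections 7.10 and 9.4 say what happens at discharge, and their silence on removal does not mean that patients stayed enrolled. The whole-stay wording can be read as continuous wear within the participation window. No document shows even one post-removal day. This stands as a limit on size. It does not settle the matter, because the operating text taken literally keeps a patient enrolled after removal and the SAP reports no check.

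Two further objections stand. The bias is not one-directional, since transfer and early discontinuation can shorten the SAP's window. Also, 13.2 sets no condition that the patient be on PUP after initiation, so restricting exposure to monitored time would be a new definition and not a correction.

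A reader might infer that the 163 surplus entries each hide time off fall-risk status. The documents do not support that: the only explanation given is technical error, and no gap lengths are reported. A reader might also infer that 1.04 is known to be too low. That does not follow either, because f could be zero and the opposite error is possible.

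**Conclusion.** The concern holds in conditional form. The SAP's exposure window is not the one 13.2 defines, and the documents do not show that the two coincide. Post-removal days, or off-status or out-of-hospital time bridged between entries, would make 1.04 too low. Un-enrolment before the 13.2 endpoint would make it too high if no falls occurred in the missing time. At assumed excess shares of 10% to 30% the bound is 1.16 to 1.49 per 1000; those shares are illustrative.

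It would be wrong to infer that the comparison with 4 per 1000 is overturned, since that needs about 74% of the days to be excess. This robustness covers the denominator question only. It says nothing about how falls were ascertained or whether the historical rate is comparable. What is at stake is the accuracy of a reported primary number and an unlabelled difference from the protocol.

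**What to change.** - **SAP exposure rule.** End each patient's exposure at the earlier of removal from fall-risk status or discharge, using times from the hospital record. Count falls over the same window.
- **Patients with several entries.** Keep gaps due to technical error within one fall-risk stay. Exclude time off fall-risk status and time between separate admissions. Do not restrict the primary definition to time on PUP.
- **Recompute** the bound and the test.
- **If the times cannot be recovered,** state that the enrolment-to-un-enrolment window departs from 13.2. Report a sensitivity range, for example 1.04 to 1.49 per 1000 for 0% to 30% excess days, and note that early un-enrolment acts in the opposite direction.
- **Protocol wording.** Align the un-enrolment text in the method of use, 7.5, 7.10 and 9.4 with the 13.2 stop rule. The SAP reports an analysis already run, so this change alone does not alter the collected data.

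The cost is one hospital-record extract, a recalculation and some wording, and probably a slightly higher upper bound.
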